The visit will be conducted in the OCTRI inpatient research unit. A code cart is on site at all locations and a code team is available by page at all times. After arrival at the clinic, women of childbearing potential will receive a urine pregnancy test if the last pregnancy test was more than 7 days prior. This test must be negative before further participation is allowed.

The subject will be asked to check his/her CBG before driving to the clinic and to bring a snack in the car in case hypoglycemia does occur (in which case, the subject must park and treat the hypoglycemia). The subject will arrive at the research center at approximately 7am.

When they arrive, a capillary blood glucose (CBG) will be obtained and measured by a Contour Next glucose meter. Subjects will be given 15-20 grams of oral carbohydrate if the CBG reading is less than 70 mg/dl. CBG values > 300 mg/dl will be managed at the discretion of the investigator with a correction bolus. If carbohydrates or a correction insulin dose is given, blood glucose will be monitored according to the study investigator's orders until the glucose is acceptable to the investigator, and is within the range of 70-300 mg/dl. Serum ketones will also be checked. If the blood ketone value is 0.6 mM or less, the procedure will be started. If serum ketones are ≥ 0.6 mM, the study will be halted and insulin therapy will be guided by the onsite investigator. Ketones will be measured with the Precision Xtra ketone meter. The Precision Xtra meter will undergo quality control testing every 30 days with two different ketone levels, one high and low and both values must fall within the accepted range for a meter to be used.

Subjects will have a Dexcom G5 sensor inserted. The wire glucose sensor is sterile and commercially available from DexcomTM and will be used for single use only as directed by the manufacturer. The sensor will be inserted into the subcutaneous tissue of the abdomen or flank after appropriate preparation of the abdominal skin as per the manufacturer's directions. Subjects will be instructed to discontinue the use of acetaminophen for all periods when wearing the Dexcom CGM system.

[figure not shown]

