At approximately 6pm, the closed-loop study will be terminated and the subject’s own insulin pump will be restarted. The IV catheter will be removed. The study investigator will consult with the subject regarding appropriate insulin dosing for the remainder of the day. The HR monitor and Dexcom G5 sensor will be removed. The glucose sensing cannula units will be slowly removed and the sensor data uploaded. Only trained personnel will be allowed to remove the devices. The personnel who will be allowed to remove the devices will include the investigators (PI, Co-I) and the clinical coordinator. The infusion sites and sensor site will be inspected for signs of erythema/edema and assessed using the Draize Scale (see Appendix F). In addition, the Dexcom G5 sensor and glucose sensing cannulas will be inspected for the possibility of breakage or fracture. If there is any evidence of sensor breakage, it will be recorded. A de-identified photograph will be taken of the sensor insertion areas and the devices. If an area of inflammation of 1 cm or greater exists around the point of insertion, the subject will return 1-3 days later for a follow-up visit.

Due to the fact that the subject’s usual diabetes routine has been interrupted, it is recognized that this final period of time represents an important period for subject safety. As the subject departs from the study center, it will be important for the subject to monitor blood glucose frequently and to be able to call the study physician if questions arise. More specifically, in order to be discharged, subject’s blood glucose must be greater than 90 and less than 300 and the subject

must be feeling well without nausea or other symptoms. If glucose is less than 90, he will be given 15 grams of rapidly acting oral carbohydrate. CBG will be repeated every 15 minutes (with repeat oral carbohydrate treatment if CBG < 90) until CBG exceeds 90, at which time the subject will be discharged.

If blood glucose exceeds 300, the study physician will determine a correction dose of insulin after evaluating the current insulin-on-board value. In addition, blood ketones will be measured. If the ketone value is over 3 mM, the subject will be sent to the OHSU Emergency Department. If the ketone value is between 0.6 and 3.0, the study physician will administer a correction dose, provide oral hydration, and keep measuring blood ketones hourly. The subject will be discharged only when the ketone value is less than 0.6 mM.

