A research staff member will telephone the subject the next day to check on health status.

If a study visit is stopped prematurely, such as due to technical problems, the subject will be asked if they can repeat the study visit that was terminated early with additional compensation provided. Repeating the study visit will be optional.

Hypoglycemia Treatment Guidelines

- **BG < 70 mg/dl**
 - Give 15 grams of oral carbohydrate.
 - Repeat treatment every 15 minutes as needed to raise blood glucose ≥ 70 mg/dl.
- **BG < 50 mg/dl**
 - Verify that insulin pump is turned off
 - Give 100 mL of 10% dextrose through the IV cannula
 - Repeat BG measurement after dextrose infusion complete and repeat process until BG > 70 mg/dl.
 - If no IV access available, give 30 grams of oral carbohydrate, further treatment as per study investigator.
- **Presence of STUPOR, LOSS OF CONSCIOUSNESS, or SEIZURE**
 - Give 1 mg glucagon SC or if IV cannula is patent, 100-300 mL of 10% dextrose STAT. Glucagon will be administered by needle and syringe that are provided with GlucaGen emergency kits.
 - Verify that insulin is turned off.
 - Further management per study investigator.

Hyperglycemia Treatment Guidelines

If the sensed glucose is ≥ 300 mg/dl for longer than 30 minutes or reaches >400 mg/dL, the subject will be instructed to check their blood glucose and study staff will examine the insulin infusion site and will check the subject's serum ketones every hour while sensed glucose is ≥ 300 mg/dl. If serum ketones are over 0.6 mM, the on call study investigator will be alerted to discuss proper management, including changing insulin infusion set and delivering a correction bolus. In addition, the subject will be encouraged to drink sugar-free liquids. If serum ketones are above 1.5 mM at any time, the study will be stopped and insulin will be administered as directed by the on call investigator.

Cleaning and Disinfecting

All devices will be cleaned and disinfected between subjects. The smart phone, Dexcom G5 transmitter, the glucose sensing cannula insertion devices and telemetry units are cleaned by study staff. Technicians who are disinfecting units will wash hands thoroughly and wear gloves. All items will undergo intermediate-level disinfection using SANI-CLOTH AF3 Germicidal disposable wipes. The disinfectant will be applied and allowed to air dry. After disinfection, when the units are completely dry, they will be placed in a sealed bag labeled with subject information.

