
Stopping Rules

The subject may withdraw at will at any time or at the discretion of the Investigator.

A subject must be withdrawn if any of the following applies:

1. Hypoglycemia: After initial stabilization, one episode of severe hypoglycemia (requiring the assistance of another person) or one episode of venous blood glucose < 50 mg/dl.
2. Hyperglycemia: After initial stabilization, venous blood glucose > 400 mg/dl for over 30 minutes.
3. Ketoacidosis: Venous blood glucose > 250 mg/dl accompanied by serum ketone level > 1.5 mM.
4. Protocol deviation having influence on efficacy or safety data as judged by the Investigator.
5. Substantial and repeated non-compliance with trial procedures
6. Pregnancy
7. Intention of becoming pregnant

The study may be stopped if the glucose sensing cannulas have repeated inability to acquire sensor data, such as telemetry issues.

Data Analysis

Note that it was not possible to carry out a formal sample size power analysis for this feasibility study since data have not previously been obtained in humans (variance is unknown). However, we expect the sample size proposed here (10) is adequate to detect a difference between the insulin formulation and saline, based on our earlier studies in swine. The data obtained in this study will be used to calculate variance so that formal power analyses can be used for subsequent, more formal, studies.

This study design will allow a comparison of sensing accuracy after insulin vs after saline administration through the sensing cannula. For example, this study design will allow assessment of the magnitude of artifact, if any, from the insulin preservatives, as was noted in pig studies with the non-redox mediator sensor. It will also assess the potential for underestimation of glucose due to uptake into fat as a result of local insulin delivery [19], [20].

For each subject, we plan to acquire data from the PDT sensor which is represented by an

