Appendix B: Alert Manager Specifications

Alarm #	Description of Alarm	When Alarm is Considered Serviced	Instructions for Subject	Alarm Refractory Period (minutes)	Alarm pushed to Study Coordinator	Alarm pushed to Study Investigator
2	ARD \geq 35% for BG \geq 75	Calibration detected	Sensor inaccuracy has been detected, please calibrate sensors with most recent blood glucose value.	30	If refractory period expires	If refractory period expires two or more times in a row
4	CBG \leq 40 mg/dl	NA	CBG is low. Please treat with 30 g of carbs and recheck CBG in 15 minutes.	NA	instantly	instantly
5	CBG < 70 mg/dl and Alert 4 is not active	Rescue carb treatment identified	Blood glucose less than 70 mg/dL, treat with 15-20 g of carbohydrate and recheck in 15 minutes.	30	If refractory period expires	If refractory period expires two or more times in a row
6	Sensor < 70 mg/dl without exercise detection and < 85 mg/dl with exercise detection and no BG given within 15 minutes and alert 5 inactive	Blood glucose value is entered	Sensor is less than 70 mg/dL. Please check blood glucose.	30	If refractory period expires	If refractory period expires two or more times in a row
7	CBG >300 mg/dl	NA	CBG is greater than 300 mg/dl. Please	NA	instantly	instantly

			change the insulin infusion and check your ketones.			
8	Sensor glucose \geq 300 mg/dl and no BG given within 30 minutes and alert 7 inactive	Blood glucose value is entered	Sensor glucose is greater than 300 mg/dl, please check and enter blood glucose, and check insulin pump for malfunctions	30	If refractory period expires	If refractory period expires two or more times in a row
9	Insulin pump communication issue	Autoservices if pump communication is restored	Insulin pump communication issue, please check pump and contact study physician	60 minute initial fire, 20 minute refractory	If refractory period expires during daytime hour of 07:00-22:59 (no nighttime escalation 23:00-06:59)	If refractory period expires two or more times in a row during daytime hour of 07:00-22:59 (no nighttime escalation 23:00-06:59)
10	Insulin meal bolus failure	Clears itself either after the meal flag is older than backlog of 15 minutes or there is not a backlog of insulin to deliver	Insulin meal bolus failed to deliver, please contact the study physician.	20	If refractory period expires	Coordinator will call subject and determine issue and consult with investigator to determine if subject should give bolus open loop.

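### Withdrawal for ketoacidosis applies from venous glucose above 250 mg/dl, but after arrival no blood glucose of 250–300 mg/dl triggers a ketone test

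*Combined protocol and SAP*

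**What the plan says.** Stopping Rules, item 3, makes withdrawal mandatory for "Ketoacidosis: Venous blood glucose > 250 mg/dl accompanied by serum ketone level > 1.5 mM".

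Ketones are to be measured in four situations:

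- **Arrival** (12 hour Treatment Visit). I read this check as applying to every subject: "If the blood ketone value is 0.6 mM or less, the procedure will be started".
- **During closed loop** (Hyperglycemia Treatment Guidelines). The condition is "If the sensed glucose is ≥ 300 mg/dl for longer than 30 minutes or reaches >400 mg/dL". Staff then check "serum ketones every hour while sensed glucose is ≥ 300 mg/dl".
- **Alert 7** (Appendix B). When a capillary glucose (CBG) above 300 mg/dl is entered, the subject is told to "change the insulin infusion and check your ketones".
- **Discharge** (12 hour Treatment Visit). To leave, the subject's "blood glucose must be greater than 90 and less than 300", and the subject must feel well. The ketone measurement sits in the next paragraph, which opens "If blood glucose exceeds 300, the study physician will determine a correction dose of insulin". The requirement for ketones below 0.6 mM closes that same paragraph.

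Two further rules stop the study visit, or define severe hyperglycemia, when ketones exceed 1.5 mM whatever the glucose (Hyperglycemia Treatment Guidelines; Monitoring Procedures). Neither orders a measurement.

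**The concern.** The protocol treats 250 mg/dl as the glucose level above which raised ketones end participation, yet it does not look for ketones until about 300. Within that band the withdrawal rule mostly has nothing to act on.

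This matters more here than in an ordinary pump study. During closed loop all insulin goes through an investigational cannula, and the subject's own infusion set has been removed. The one ketone value every subject has was taken before that switch, so it says nothing about delivery through the new device.

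Two other rules depend on the same missing value. Monitoring Procedures counts hyperglycemia as an adverse event only with positive ketones or listed events such as hospitalization. It also counts ketones above 1.5 mM as severe hyperglycemia, and two subjects stopped for severe hypoglycemia or severe hyperglycemia halt the whole study. Ketosis in an untested subject at 251–299 mg/dl would enter neither.

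**Working it through.** The plan gives no figure to reproduce. The check sets each ketone instruction against the 250 mg/dl floor of item 3.

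| Instruction | Measurement it reads | Trigger | Acts on blood glucose above 250 and up to 300? |
|---|---|---|---|
| Arrival check | none needed | every subject | Yes, but before closed loop |
| Hyperglycemia Treatment Guidelines | Dexcom G5 | ≥ 300 for > 30 min, or > 400 | No |
| Alert 7 | entered CBG | > 300 | No |
| Alert 8; Risks section | Dexcom G5 | ≥ 300; > 300 | No; these order a glucose check only |
| Discharge | blood glucose | > 300 | No |

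In the band, a ketone value can arise in three ways: the Dexcom reads 300 or more for long enough, an earlier value above 300 is still being followed, or an investigator chooses to test. The first route closes when closed loop ends: "The HR monitor and Dexcom G5 sensor will be removed". The written trigger for discharge is then blood glucose above 300, while the discharge window admits 251–299.

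**Age of the last ketone value.** Arrival is at about 07:00 and closed loop ends at about 18:00, so 18 − 7 = 11 h. Closed loop itself starts at 09:30, so the untested time on the cannula is 18:00 − 09:30 = 8.5 h.

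**Dependence on sensor error.** The protocol calls a sensor inaccurate at a difference of 35% or more from a CBG. All the errors below are within that tolerance.

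- Over-reading needed to show 300: at venous 251, 300/251 = 1.195, or 19.5% high; at venous 280, 300/280 = 1.071, or 7.1% high.
- Under-reading that hides a true value above 300: at venous 350, 1 − 300/350 = 14.3% low; at venous 390, 1 − 300/390 = 23.1% low. A sensor 25% low at 390 shows 0.75 × 390 = 292.5 mg/dl.

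The under-reading examples lie above the 250–300 band. They show a related weakness: the guideline trigger reads only the sensor, although venous glucose is drawn every 15 minutes. At venous 300–400 a low sensor leaves that trigger off unless the value is entered as a CBG and sets off Alert 7. Above 400 for over 30 minutes, item 2 of the Stopping Rules requires withdrawal.

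**Upper bound on added tests.** Assume a subject is above 250 from the first sample at 09:30 and is confirmed at 09:45. Hourly checks from 09:45 to 17:45 make 9, and one at discharge makes 10. For 10 subjects that is 10 × 10 = 100.

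**The case against.** The strongest reply is that a withdrawal definition is not a testing schedule. A floor of 250 still does some work: it catches a subject whose sensor reads 300 or more while venous glucose is lower, or one being followed down from above 300. The protocol uses about 300 consistently as its action level, and nothing in it shows that 250 is the right level for testing. Two meals of 80–150 g carbohydrate with a nominal 80% bolus will produce excursions, so a reading above 250 may simply be post-meal.

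There are also other protections. The controller raises insulin for high glucose, staff are present throughout, cannula patency is checked after insertion, and alerts flag pump communication and delivery failures. Investigators may change the protocol for safety. At the end the subject's own pump is restarted, an investigator advises on dosing, the subject must feel well, and staff telephone the next day.

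Much of this stands as context. The thresholds do not contradict each other, high glucose itself is seen and acted on, and the benefit of testing at 250 cannot be quantified from the documents. But none of these protections supplies a ketone value. Discretion allows a test without requiring one, and the stops at 1.5 mM at any time need a result that nobody has been told to obtain. The 0.6 mM discharge line cannot be read as covering everyone, because no measurement is ordered at or below 300. That late readings above 250 may be common after a 15:00 lunch makes a written rule more useful.

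**Conclusion.** The concern holds. After arrival, no blood glucose above 250 and up to 300 mg/dl triggers a ketone test. A symptom-free subject at 251–299 who never met a trigger satisfies every written discharge condition with a ketone value about 11 hours old.

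This rests on two readings of the text: that the arrival check applies to all subjects, and that the 0.6 mM discharge condition belongs to the paragraph on glucose above 300. I am confident of the threshold comparison. How many readings or subjects will fall in the band, and how many of those would have ketosis, is not given and I do not estimate it. The point concerns safety monitoring and adverse-event capture. It does not touch the primary endpoint or its analysis. I class it as an inexpensive improvement.

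**What to change.** Make two wording changes.

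1. **Hyperglycemia Treatment Guidelines.** Alongside the sensor trigger, require a ketone check when the 15-minute venous glucose exceeds 250 mg/dl, for example once confirmed on the next sample, then hourly while it stays above 250. This also removes the dependence on sensor error at 300–400.
2. **Discharge paragraph of the 12 hour Treatment Visit.** Require a ketone value below 0.6 mM before discharge whenever blood glucose exceeds 250 mg/dl, and apply the steps already written there if it is higher.

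Raising item 3 to 300 would align the numbers but add no test in the band, so I advise against it.

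The cost is extra strips on the Precision Xtra meter already in use, with an upper bound of 10 scheduled tests per subject and 100 for the study, possibly with some extra fingersticks. A subject ending the visit above 250 may stay a little longer. One found at 0.6–3.0 mM would have a correction dose, oral hydration and hourly retests until below 0.6 mM. Those retests come on top of the bound, and the delay could be more than slight.

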- To assess the glucose control achieved in adults with type 1 diabetes with the use of the OHSU closed-loop system.
- To assess the tolerability of the PDT glucose sensor.

Study Hypothesis:

We propose that the accuracy of the PDT glucose sensor is not impacted by the delivery of lispro insulin as compared to a saline placebo.

Endpoints**Primary Endpoints**

- Sensor accuracy as determined by mean absolute difference (MAD) for reference YSI venous blood glucose values ≤ 75 mg/dL and mean absolute relative difference for reference YSI venous blood glucose values >75 mg/dL

Secondary Endpoints (duration: entire study):

- Percent of time with sensed glucose between 70 – 180 mg/dl (based on Dexcom G5 CGM)
- Percent of time with sensed glucose <70 mg/dL (based on Dexcom G5 CGM)
- Percent of time with sensed glucose <54 mg/dl (based on Dexcom G5 CGM)
- Percent of time with sensed glucose >250 mg/dL (based on Dexcom G5 CGM)
- Mean sensed glucose (based on Dexcom G5 CGM)
- Number of carbohydrate treatments (defined as 15 or 20 grams of carbohydrate)
- Total amount of insulin delivered (in units/kg)

- Mean score on visual analog scale at 15 and 120 minutes after insertion, and at end of study
- Mean score on Draize scale at end of study

Study Type

This is a single center, one treatment trial designed to compare the sensor accuracy of the PDT sensing catheter when utilized to deliver lispro insulin as compared to a saline control.

Study Population

Study population will be adults with type 1 diabetes, ages 21 – 65 years of age. Younger subjects are excluded as it is appropriate to assess safety first in the adult population. 10 subjects will be recruited to participate in studies.

Power Analysis

Since data have not previously been obtained in humans (variance is unknown), this study is exploratory and not powered.

Protocol Summary:

[figure not shown]
Subjects will undergo one 12 hour inpatient study. During this intervention visit, subjects will wear two t:slim insulin pumps to deliver insulin or saline through two investigational PDT glucose sensing cannulas, and a Dexcom G5 CGM to measure glucose. The subject will come to

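### The statement that 10 subjects are adequate to detect an insulin–saline difference is unquantified, and the plan then reads p > 0.05 as showing no difference

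*Combined protocol and SAP*

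**What the plan says.** The Study Population section sets the size: "10 subjects will be recruited to participate in studies". The Power Analysis section then says: "Since data have not previously been obtained in humans (variance is unknown), this study is exploratory and not powered".

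The Data Analysis section opens by repeating that "it was not possible to carry out a formal sample size power analysis for this feasibility study", for the same reason. Its next sentence says "we expect the sample size proposed here (10) is adequate to detect a difference between the insulin formulation and saline", and gives as its basis "based on our earlier studies in swine". It reports no swine effect size, SD, number of animals or power. The one swine finding described anywhere is a preservative artifact, "as was noted in pig studies with the non-redox mediator sensor", with no magnitude.

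Later in the same section, a calibration line is fitted for each subject and each catheter, and the slopes and intercepts are compared between insulin and saline catheters by a t-test. The plan does not say whether the test is paired or two-sided. A p-value above 0.05 is to be taken as the sign that the null hypothesis of identical means is true. That null hypothesis is also what the study hopes to show: the Background and Study Hypothesis sections both predict that lispro does not affect sensing accuracy. No equivalence margin is given.

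**The concern.** Adequacy to detect a difference is a statement about power. It needs a difference, an SD and a target power, and the plan supplies none of them. It also says that the human SD is not available.

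In most feasibility studies one optimistic sentence about sample size would do little harm. Here it supports the main inference. The study hopes for a null result and counts a non-significant t-test as confirmation. The only reason the plan offers for trusting such a result is that 10 subjects would have revealed a difference had there been one. If that cannot be checked, a non-significant test could be reported as evidence that lispro leaves the sensor unaffected when the data are also compatible with a shift that matters.

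**Working it through.** **Inputs from the documents.** 10 subjects, each wearing one lispro and one saline sensing cannula (Study Population; Protocol Summary), hence 10 within-subject pairs. Significance threshold 0.05 (Data Analysis). Effect size, SD, power, equivalence margin and dropout rate: not given.

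**Assumptions.** Two-sided 5% test, normally distributed differences, 10 evaluable pairs. The paired test is the natural one for this design, but the plan says only that a t-test will be used, so the unpaired case is shown as well.

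**Reproducing the plan's figure.** This cannot be done. Without an effect size, SD and power, the figure of 10 can be neither reproduced nor refuted. What can be calculated is what 10 pairs deliver in SD units.

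**Power, paired.** Let δ be the true mean difference divided by the SD of the within-subject differences. The test statistic follows a noncentral t with 9 df and noncentrality δ√10. Power is the probability that it falls outside ±t(0.975, 9) = ±2.262. At δ = 0.5, the noncentrality is 0.5 × 3.162 = 1.58 and power is 29.3%, so p > 0.05 occurs in 100 − 29.3 = 70.7% of trials.

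**Power, unpaired.** With 10 values per arm treated as independent, df = 18 and the noncentrality is δ√(10/2). Here δ is in units of the SD between subjects within an arm, so the two power columns are not directly comparable.

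| True shift (SD units) | Power, paired | Chance of p > 0.05, paired | Power, unpaired |
|---|---|---|---|
| 0.2 | 8.8% | 91.2% | 7.1% |
| 0.3 | 13.6% | 86.4% | 9.7% |
| 0.5 | 29.3% | 70.7% | 18.5% |
| 0.8 | 61.6% | 38.4% | 39.5% |
| 1.0 | 80.3% | 19.7% | 56.2% |
| 1.5 | 98.7% | 1.3% | 88.7% |

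**Detectable shift.** Paired: 0.996 SD for 80% power and 1.155 SD for 90%. Unpaired: 1.325 SD for 80%.

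**Precision, paired.** The 95% CI half-width is t(0.975, 9)/√10 = 2.262/3.162 = 0.715 SD.

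**Equivalence.** Suppose no effect were instead shown by two one-sided tests (90% CI inside a margin), with a true difference of zero. The margin would have to be about 1.0 SD for 80% power (simulation, 400,000 draws).

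**Scope.** These figures apply to one test. The plan has two, on slope and intercept. The chance that both are non-significant depends on the size of each shift and their correlation, which the documents do not give.

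**The case against.** The strongest defence has four parts.

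- *The statements are compatible.* Having no formal human power calculation while holding an informal expectation from animal work is not a logical contradiction, and the sentence is hedged as an expectation. This stands. A reader might infer that the sections flatly contradict each other or that no basis was offered; the documents support neither. A basis is named, but it carries no figures.
- *The claim may be right.* If the artifact in humans is about 1 SD of the within-subject differences or more, 10 pairs are enough. This also stands: the claim is not shown to be false.
- *A large standardised effect need not be large in practice.* It is tempting to say that only very large effects could be detected. The documents do not support that. The SD is unknown, so 1 SD could be small or large in mg/dL per nA, or relative to the artifact seen in pigs.
- *Readers are warned.* The study is called exploratory and a feasibility study, and its data are meant to supply the variance for later power analyses. This is a fair answer to any demand for a power calculation, and none is made here. It does not answer the p > 0.05 rule, which draws a firm conclusion from a test whose sensitivity the plan says it cannot state.

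The harm does arise mainly from that rule. Deleting the adequacy sentence alone would leave the rule standing, so the two passages have to be changed together.

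**Conclusion.** The point holds as one about an unquantified claim joined to a decision rule that depends on it. The plan gives no means of checking that 10 subjects are adequate, and it says that the quantity needed for the check is unknown. Under a two-sided 5% paired t-test with 10 evaluable pairs and normal differences, the study has 80% power only for a true difference of about 1.0 SD of the within-subject differences. It would miss a 0.5 SD shift about 71% of the time, and the current rule would read each miss as support for no lispro effect. An unpaired analysis would need about 1.3 between-subject SDs for 80% power.

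The figures are in SD units because the documents give no SD. They describe the slope and intercept tests; no test is named for the primary accuracy endpoint (MAD and MARD). They do not show that the sample size is wrong for a feasibility study.

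**What to change.** Make two linked changes in the Data Analysis section.

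1. Delete the adequacy sentence. State instead that, with a two-sided 5% paired t-test and 10 evaluable pairs, the study has 80% power only for a true difference of about 1.0 SD of the within-subject differences, with an expected 95% CI half-width of about 0.72 SD.
2. In the paragraph on slopes and intercepts, specify a paired t-test, report the paired mean difference with its 95% CI for each parameter, and remove the rule that p > 0.05 shows the null hypothesis to be true.

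This also brings the section into line with the Power Analysis section. No subjects, procedures or data are added. The cost is that the stated property becomes less favourable, and the study can no longer claim absence of a lispro effect from a non-significant test alone.
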